4.5.1.2 Statistical Hypothesis, Model, and Method of Analysis

Changes in WURSS-21 domain and total scores from baseline will be analyzed using a linear mixed-effects model for repeated measures (MMRM) with subjects as the clustering unit. The model will include treatment day (as a categorical variable up to day 7) and baseline WURSS-21 score as fixed effects, with a random intercept for each subject. The model will employ an unstructured covariance matrix for within-subject variance-covariance errors, Kenward-Rogers degrees of freedom, and restricted maximum likelihood estimation (REML). For each treatment group, the following will be reported at each treatment day: estimated marginal mean differences from baseline on the original scale, standardized effect sizes (where applicable) with 95% confidence intervals, and nominal p-values. Primary endpoints will be evaluated at the 5% significance level. Given the study design, no adjustments for multiple comparisons will be made.

The distribution of outcome measures will be assessed for normality using Q-Q plots for each treatment group. While linear mixed-models are generally robust to modest departures from normality, substantial deviations (as assessed through visual inspection of Q-Q plots and formal tests including Shapiro-Wilk test) will prompt complementary analyses using

non-parametric methods. The Wilcoxon signed-rank test will be conducted at each timepoint, including end of treatment, as a sensitivity analysis to the primary MMRM analysis. If substantial discrepancies (defined as >20% difference in effect estimates or divergent statistical significance at $\alpha=0.05$) are observed between the MMRM and Wilcoxon signed-rank test results, both sets of results will be reported with appropriate discussion of the differences. For the primary analysis, the MMRM results will be considered primary, with non-parametric results serving as supportive evidence. Model diagnostics will include assessment of heteroscedasticity through residual plots. If significant heteroscedasticity is detected (defined as systematic patterns in residual plots or significant Breusch-Pagan test results at $\alpha=0.05$), Huber-White robust standard errors will be applied to ensure valid inference. All model assumption violations and remedial measures will be documented in the statistical analysis report.

For each domain and item, the value at each timepoint and corresponding change from baseline and % improvement will be summarised descriptively for each treatment group. Raw means (with standard deviations) for each endpoint at each assessed timepoint (day 1-7) will be plotted by treatment group. Change from baseline to end of treatment, as defined as either the last day subject uses study product or day 7 (whichever event comes first), will also be calculated and presented. Each WURSS-21 domain and individual item will be analyzed with comprehensive summary statistics presented by treatment group at each timepoint (Days 1-7) and at end of treatment (defined as either the last day of study product use or day 7 (whichever event comes first)). These statistics will encompass observed values, including mean, standard deviation, median, interquartile range, and 95% confidence intervals. Additionally, changes from baseline will be characterized through mean change, standard deviation of change, median change, and 95% confidence intervals for mean change, along with percent improvement calculations including mean percentage, standard deviation, median percentage, and associated confidence interval. Longitudinal profile plots, which will display mean values and mean changes from baseline (both with ± 1 standard error) over time by treatment group, will be provided. Median values and interquartile ranges will also be plotted to provide a complete assessment of distributional characteristics throughout the study period.

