### 8.3.2 Primary Endpoint Analysis(es)

For the primary objective, measurements of health related QoL indicators and cold symptoms will be evaluated using daily WURSS-21 scores (total scores, total QoL domains scores, total symptom domains scores, and single symptom and QoL domains scores) change from baseline to each treatment day to determine the effectiveness of the two treatment groups (Daytime, Daytime+Nighttime).

Change from Baseline in mean WURSS-21 scores to each treatment day will be summarized and analyzed using a mixed-effects model for repeated measures (MMRM) with treatment, treatment day as a discrete variable, and applicable baseline WURSS-21 scores as fixed effect and a random intercept for each subject. Estimated marginal mean differences between baseline and each treatment day will be reported by treatment group including the mean difference on the original scale, standardized effect size including 95% confidence intervals (CI), and the respective p-value. The distribution of each outcome is assessed using Q-Q-plots by treatment group. In case of apparent deviations from the normal distribution, the changes from baseline are assessed using a Wilcoxon signed-rank test.

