1.2 Study Objectives

Each of the treatment groups will be analyzed separately; there is no comparison between the study groups (daytime product only and daytime/nighttime product combination).

Objectives	Endpoints
Primary Objective	Primary Endpoint
To evaluate the over-time effects of Robitussin on QoL factors and common cold symptoms among individuals	Score change from Baseline to each treatment day in: 
• WURSS-21 total score

Haleon Confidential

CCI Statistical Analysis Plan template v7.0

Objectives	Endpoints
experiencing cough associated with common cold, following up to 8 days of treatment using WURSS-21.	
 • WURSS-21 total symptom domain score • WURSS-21 total QoL domain Score • Each of the WURSS-21 symptom scores (10 items in total) [a] • Each of the WURSS-21 QoL scores (9 items in total)
Secondary Objectives	Secondary Endpoints
To evaluate the over-time effects of Robitussin on QoL factors among individuals experiencing cough associated with common cold, following up to 8 days of treatment, using specific QoL questions.	Score change from Baseline to each treatment day in: 
 • social activities • feeling self-conscious around people • coughing in public • falling asleep • sleeping through the night • energy • motivation
To evaluate the over-time effects of Robitussin on specific QoL questions among individuals experiencing cough associated with common cold, following up to 8 days of treatment, using categorized QoL factors.	Score change from Baseline to each treatment day in: 
 • Sleep quality • Vitality • Physical activities • Social activities
Safety	
To record adverse events (AEs) during study period	Number and percent of patients reporting AEs or serious AEs (SAEs) while on treatment: 
 • Related to product • Not related to product
Exploratory Objectives	Exploratory Endpoints
Subgroup analyses for primary and secondary endpoints.	Subgroup: Exclude subjects who took concomitant medications that are known to have an impact on common cold symptoms

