4.5 Analysis

4.5.1 Primary Endpoint

4.5.1.1 Primary Endpoint Definition

The primary endpoint will be measured using the Wisconsin Upper Respiratory Symptom Survey (WURSS); 21 question daily symptom report.

WURSS-21 scores will be reported as:

- Total score: sum of questions 2 through to 20
- Total symptoms domains score: sum of the items (questions 2 – 11) in the symptom section (10 individual items on cold symptoms answered on a 0 (does not have this symptom) - 7 (severe scale))
- Total QoL domain score: sum of the domains (questions 12 – 20) in the QoL section (9 individual items on cold interference to QoL answered on a 0 (not at all) - 7 (severely scale))
- Individual symptom item score (10 items)
- Individual QoL item score (9 items)

Change from baseline (Day 0) will be calculated for each subject by subtracting the baseline score from scores at subsequent treatment timepoints (Days 1-7 after baseline) regardless of study product use compliance as long as they have used it at least once and at end of treatment (defined as the last day of study product use or day 7 – whatever event comes first). The percentage improvement will be calculated at each timepoint (Days 1-7, and end of treatment), any timepoints after Day 7 will not be included in the analysis tables but will be included in the subject listings. Results will be presented for both the mITT and NCCM populations in:

- Tables 14.2.1.1.1 through 14.2.1.5.2
- Figures 14.2.3.1 through 14.2.6.2

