4.6 Analysis of Secondary Objectives

4.6.1 Secondary Endpoint: Specific QoL Scores

Measurements of health related QoL indicators will be evaluated using the specific QoL scores and categorized QoL scores change from baseline to each treatment day to determine the effectiveness of the two treatment groups (Daytime, Daytime+Nighttime).

The Specific QoL Scores consist of 7 separate questions on QoL, scored 0 ('not at all') to 7 ('severely'). Lower scores represent better outcomes. Each specific question covers one of the following topics:

- Social activities
- Feeling self-conscious around people
- Coughing in public
- Falling asleep
- Sleeping through the night
- Energy
- Motivation

Changes from baseline in Quality of Life (QoL) domain scores (Sleep Quality, Social Activities, Physical Activities, and Vitality) will be analyzed longitudinally using the same methodological approach as the primary outcome. The analysis will be conducted for the mITT population, with results presented in Tables 14.2.2.1.(1-2) and Figures 14.2.4.(1-2); 14.2.5.(1-2). A linear mixed-effects model for repeated measures (MMRM) will be fitted separately for each QoL domain. Each model will include treatment day as a categorical fixed effect, baseline QoL score as a continuous covariate, and a random intercept for subject to account for within-subject correlation. The models will employ an unstructured covariance matrix, Kenward-Rogers degrees of freedom adjustment, and restricted maximum likelihood estimation (REML) to ensure valid inference. For each QoL domain and treatment group, the following estimates will be reported at each timepoint: estimated mean changes from baseline with 95% confidence intervals, between-treatment differences in mean changes with 95% confidence intervals, standardized effect sizes (Cohen's d) with 95% confidence intervals, and associated p-values for treatment comparisons. Statistical significance will be evaluated at $\alpha=0.05$ level. Given the exploratory nature of the QoL analyses, p-values will be reported without adjustment for multiplicity, but interpretations will consider the potential impact of multiple testing on Type I error rates. Sensitivity analyses for the robustness of results to missing data and distributional assumptions will follow the same approach as specified for the primary outcome.

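### The primary within-arm 95% intervals and 5% tests hold only conditional on the observed baselines, because each change is adjusted for its own baseline

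*SAP*

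**What the plan says.** The outcome is a raw difference (SAP 4.5.1.1): "Change from baseline (Day 0) will be calculated for each subject by subtracting the baseline score from scores at subsequent treatment timepoints". SAP 4.5.1.2 fits that difference in a repeated-measures mixed model with an unstructured covariance and Kenward-Roger degrees of freedom. On the mean structure it says: "The model will include treatment day (as a categorical variable up to day 7) and baseline WURSS-21 score as fixed effects". For each arm and day it will report "estimated marginal mean differences from baseline on the original scale, standardized effect sizes (where applicable) with 95% confidence intervals, and nominal p-values". It adds: "Primary endpoints will be evaluated at the 5% significance level". SAP 1.2 makes the inference within-arm: "Each of the treatment groups will be analyzed separately; there is no comparison between the study groups".

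Protocol 8.3.2 describes a pooled model with a treatment term, also adjusted for baseline, and has the same target: "Estimated marginal mean differences between baseline and each treatment day will be reported by treatment group". SAP 4.6.1 uses "baseline QoL score as a continuous covariate", and SAP 4.6.2 also adjusts for baseline. Both report within-arm changes with 95% intervals. Both also plan between-arm comparisons.

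Neither document says at which baseline value the marginal mean is taken, or whether its standard error allows for the baseline mean being an estimate.

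**The concern.** Baseline adjustment is routine for a difference between arms, where uncertainty in the overall baseline mean cancels. Nothing cancels it in a single arm's mean change. With complete data, the marginal mean at the sample-mean baseline equals the raw mean change, so its sampling variance is that of the raw change. The model instead uses the residual variance of change given baseline and treats the baseline mean as a known constant.

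An extreme case shows the mechanism. If everyone recovered to 0, change would equal minus baseline. The true standard error of the mean change would be SD(baseline)/√n, but the regression on baseline would leave no residual and report about 0.

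Kenward-Roger does not repair this, and neither do the Huber-White errors that SAP 4.5.1.2 allows under heteroscedasticity. Both still condition on the observed baselines. The trial has no comparator and no multiplicity adjustment, so these intervals and per-test p-values carry its primary inference.

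**Working it through.** **Inputs**
- Level 5% (SAP 4.5.1.2). Sidedness is not stated; I take it as two-sided because it is paired with 95% intervals.
- 100 completers per arm (SAP 1.4). The plan's arithmetic reproduces: 260 × (1 − 0.23) = 200.2, for two arms.
- SDs and the baseline-to-follow-up correlation ρ are not in the documents. I assume ρ from 0.3 to 0.7, and s = SD(follow-up)/SD(baseline) of 1 or 0.7.
- Complete data, with the marginal mean at the sample-mean baseline (assumed).

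**1. The plan's own 5%.** I simulated 8,000 trials per scenario (n = 100, seven days, s = 1). Tested against the mean change expected given the observed baselines, with a slope for each day, the level is 0.044–0.054. The stated 5% reproduces for that conditional target.

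**2. Population mean change, slope for each day.** Set SD(baseline) = 1.
- True variance of change: 1 + s² − 2ρs
- Variance the model uses: s²(1 − ρ²)
- r = model SE / true SE = square root of the second over the first; for s = 1 this is √((1 + ρ)/2)
- Non-coverage = 2 × (1 − Φ(1.96r)). The sample size cancels.

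| s | ρ | True variance | Model variance | r | Non-coverage | Coverage |
|---|---|---|---|---|---|---|
| 1 | 0.3 | 1.40 | 0.910 | 0.806 | 11.4% | 88.6% |
| 1 | 0.5 | 1.00 | 0.750 | 0.866 | 9.0% | 91.0% |
| 1 | 0.7 | 0.60 | 0.510 | 0.922 | 7.1% | 92.9% |
| 0.7 | 0.3 | 1.07 | 0.446 | 0.646 | 20.6% | 79.4% |
| 0.7 | 0.5 | 0.79 | 0.368 | 0.682 | 18.1% | 81.9% |
| 0.7 | 0.7 | 0.51 | 0.250 | 0.700 | 17.0% | 83.0% |

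For s = 1, non-coverage is also the actual level of the test.

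**3. The SAP's single slope across days, unstructured covariance.** Simulated with n = 100, s = 1 and zero mean change, using t with n − 2 degrees of freedom in place of Kenward-Roger:
- exchangeable ρ = 0.5: level 0.083–0.090
- exchangeable ρ = 0.7: 0.068–0.074
- first-order autoregressive 0.8: 0.056 on Day 1, rising to about 0.095 on Days 6–7
- ρ falling from 0.6 to 0.26 (separate run, 4,000 trials): 0.070 on Day 1, 0.110 on Day 7

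In the 8,000-trial runs, the raw mean change with its own standard error gives 0.046–0.053.

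**4. Where the error vanishes or reverses.** r = 1 when change is uncorrelated with baseline (ρs = 1). Protocol 4.3 requires a cough score of at least 5 on a 0–7 scale, which restricts the baseline SD. Assuming a baseline SD of 0.8, a follow-up SD of 1.5–2 and ρ of 0.2–0.5, the level for cough is 0.050–0.064. If the baseline SD is 0.8 of the follow-up SD and correlation is autoregressive, the common slope can make some days' standard errors up to 5% too large (level 0.040–0.050).

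**5. Effect on decisions.** Simulated with n = 100 and a slope for each day, the adjusted test and the paired t-test disagree in 0.1–0.9% of trials when the true change is 0.5 baseline SD, and in none at 0.75 SD. At about 0.2 SD they disagree in about 10–27%.

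**The case against.** The strongest defence is that conditional inference is legitimate, and conditional on the observed baselines the 5% holds (step 1). That stands as mathematics. However, the SAP does not declare a conditional target, and a real-world study reporting change without a comparator will be read as estimating the mean change in people with a cold.

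Second, colds resolve, so later-day changes are likely to be large and to stay significant under either method. This also stands, although the documents give no effect size. It leaves interval widths, early days and slow-moving items exposed.

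Third, SAP 4.5.1.2 already requires descriptive 95% intervals for the raw mean change and plans a Wilcoxon signed-rank test on changes. Both include baseline variation, so a valid interval will be visible. They do not correct the primary result. With complete data the same estimate would carry two different intervals, with the model-based one called primary, and the SAP's rule on diverging significance could fire because of this artefact.

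Fourth, a reader might infer that every primary and secondary result is affected. The documents do not support that: SAP 4.6.1 and 4.6.2 also plan between-arm differences, where the omitted term cancels. Only the within-arm intervals in those sections share the problem.

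**Conclusion.** The point holds and should be fixed. For the population mean change, the primary model does not guarantee the stated 5% and 95%. With equal SDs and ρ of 0.3–0.7, model standard errors are about 8–19% too small, the level is about 7–11% and coverage about 89–93%. If the follow-up SD falls to 0.7 of baseline, coverage could drop to about 79–83%. All of these figures rest on assumed SDs and correlations, complete data and evaluation at the sample-mean baseline. With complete data the point estimates are unchanged.

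Two stronger readings are tempting. One is that late-day tests have a false-positive rate of 17–21%. The smaller follow-up SD is assumed because scores shrink as colds resolve, and then the mean change is not zero, so the figure describes undercoverage rather than Type I error. The other is that the standard errors are too small for every item and day. The documents give nothing to establish that; the error is close to zero for a restricted item such as cough may be, and it can reverse slightly on some days under the common slope.

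**What to change.** For the within-arm primary results, replace the change-score model in SAP 4.5.1.2 and Protocol 8.3.2. In each arm, fit the scores at Days 0–7 as responses, with day as a categorical fixed effect, an unstructured covariance over Days 0–7 and no baseline covariate. Report Day k minus Day 0 with its 95% interval and p-value. In simulation (3,000 trials) this contrast had a level of 4.3–5.1% on every day. It is likelihood-based, so it keeps the missing-at-random handling in SAP 4.5.2 and still uses the baseline data.

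Use the same contrast for the within-arm secondary results in SAP 4.6.1, SAP 4.6.2 and Protocol 8.3.3. Handle the between-arm comparisons in SAP 4.6.1 and 4.6.2 separately: reconcile them with the statement in SAP 1.2 that the arms are not compared. If they are kept, they may retain baseline adjustment.

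The cost is revised model wording in both documents and a few lines of code. Intervals become wider, as they should: with equal SDs, by 1/0.922 to 1/0.806, or about 8–24%, for ρ from 0.7 to 0.3.

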## 4.3 Inclusion Criteria

An individual must meet all the following inclusion criteria to be eligible to be included into the study:

1. Individual provides a signed and dated electronic informed consent document indicating that the subject has been informed of and consents to all pertinent aspects of the study, before any assessment is performed and individual has reviewed and is willing to follow the product label.
2. Individual aged 18 years or older at the time of electronic consent, inclusive of all ethnicities, races and gender identities.
3. Individual reporting initiation of cough symptoms within 48 hours prior to initiation of the virtual visit.
4. Individual reporting a minimum score of 5 (moderate) for cough associated with common cold symptoms and at least one other symptom of common cold (at least mild score of 3) as per the WURSS-21 symptom domains.
5. Individual reporting at least one night's sleep has been disrupted in the previous 2 nights due to the symptoms of common cold.
6. Individual who is willing to self-treat their cough using the study treatment.
7. Individual who is in good general and mental health.
8. Individual who resides in the United States (except for Hawaii and Alaska).
9. Individual who owns a mobile device with access to stable internet connection and is willing to use their device to complete study surveys and assessments per the schedule of events.
10. Individual who has not taken any cough products containing dextromethorphan, guaifenesin, or doxylamine (e.g. Robitussin, Delsym, Vicks, Mucinex), or cough

drops/lozenges containing benzocaine or menthol (e.g. Cepacol, Halls, Ricola) or any natural cough products during the study.

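### Subject-level % improvement is planned for every WURSS-21 item and domain, but 0 is a valid baseline for 18 of 19 items and for the QoL domain, and the SAP gives no formula or zero-baseline rule

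*SAP*

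**What the plan says.** SAP 4.5.1.1 introduces the measure and its timepoints: "The percentage improvement will be calculated at each timepoint (Days 1-7, and end of treatment". SAP 4.5.1.2 applies it to all scores, by treatment group: "For each domain and item, the value at each timepoint and corresponding change from baseline and % improvement will be summarised descriptively". It then lists the statistics: "percent improvement calculations including mean percentage, standard deviation, median percentage, and associated confidence interval".

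The items are "10 individual items on cold symptoms answered on a 0 (does not have this symptom) - 7 (severe scale" and "9 individual items on cold interference to QoL answered on a 0 (not at all) - 7 (severely scale". A score of 0 is therefore an ordinary answer: no symptom, or no interference.

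Protocol 4.3 sets the only floor on baseline scores: "Individual reporting a minimum score of 5 (moderate) for cough associated with common cold symptoms and at least one other symptom of common cold", the second symptom needing a score of at least 3. That second symptom is not named. A further criterion concerns sleep: "Individual reporting at least one night's sleep has been disrupted in the previous 2 nights due to the symptoms of common cold". It is a separate self-report and sets no minimum on the WURSS-21 sleep item.

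Neither document gives a formula for % improvement or says what happens when the baseline is 0. SAP 4.5.2 rules out imputing missing values, which does not settle a division by zero.

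**The concern.** A percentage change from an individual baseline needs a non-zero denominator. Here 0 is a legitimate baseline for most of the scores concerned, so the programmer must invent a rule.

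The obvious rule, leaving those subjects out, is not neutral. A subject at 0 can stay at 0 or get worse, but cannot improve, so omission removes only non-improvers. This is plausible in practice: entry requires cough onset within 48 hours, and the limitations text in Protocol 3.2 says most patients report more symptoms within 24 hours of cold onset.

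Among the subjects who remain, improvement is capped at +100% while worsening is not, so a few low baselines can dominate the mean, SD and confidence interval.

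At stake are item-level and QoL-domain percentages that rest on different subjects from the change scores beside them, and that can show improvement or worsening when nothing has changed. Each arm is analysed separately (SAP 1.2, Protocol 8.3), so no between-arm contrast would cancel the distortion. Appendix 1 of the SAP marks the QoL domain table (14.2.1.3.1) and the QoL item table (14.2.1.5.1) as topline for the mITT population. Among symptom items only cough is topline.

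**Working it through.** The documents state no figure for % improvement and no baseline item distribution, so there is no plan figure to reproduce. The formula is assumed to be 100 × (B − F)/B, where B is the baseline score and F the Day t score.

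**1. Where the denominator can be 0.** There are 10 + 9 = 19 items. Only cough has its own floor (5), which leaves 19 − 1 = 18 items that may be 0. The QoL domain sums nine items with no floor, so it may be 0. The total and symptom domain scores are at least 5 + 3 = 8 in any subject who meets the criteria.

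**2. Limits for one item.** The best value is always +100%. The worst is 100 × (B − 7)/B: −600% for B = 1, −250% for 2, −133% for 3, −75% for 4 and −40% for 5. Take two subjects, one going 1→3 (−200%) and one 5→3 (+40%). Their mean change is 0 and their mean % improvement is −80%.

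**3. No true change, correlation 0.** Assume a share p of subjects has score 0, the rest are uniform on 1-7, and B and F are independent with the same distribution. Then E[F] = 4(1 − p) and E[1/B | B > 0] = (1 + 1/2 + … + 1/7)/7 = 0.3704. With zero baselines left out:

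mean % improvement = 100 × (1 − 4(1 − p) × 0.3704)

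- p = 0.1: 100 × (1 − 3.6 × 0.3704) = −33.3%
- p = 0.3: 100 × (1 − 2.8 × 0.3704) = −3.7%
- p = 0.5: 100 × (1 − 2.0 × 0.3704) = +25.9%

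The mean change among the evaluable subjects is 4(1 − p) − 4 = −4p, that is −0.4, −1.2 and −2.0 points. Over all subjects it is 0.

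**4. No true change, correlated scores.** Daily ratings of one cold will be correlated. The same marginal distribution was used on both days, through a latent bivariate normal with correlation r:

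| r | 10% zeros | 30% zeros | 50% zeros |
|---|---|---|---|
| 0 | −33.3% | −3.7% | +25.9% |
| 0.3 | −25.5% | −5.7% | +15.5% |
| 0.5 | −19.8% | −6.1% | +9.4% |
| 0.7 | −13.1% | −5.5% | +4.1% |

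The percent change of group means, 100 × (mean B − mean F)/mean B, is 0% in every cell. The median is not a cure: at r = 0.5 it is 0%, 14.3% and 33.3% for 10%, 30% and 50% zeros. A simulation with r from 0.3 to 0.7, zeros from 0% to 50% and flat, mostly low or mostly high non-zero scores gave means from −34.5% to +27.0%, with SDs of 50 to 129 points. The percent change of group means stayed within 0.2 points of 0.

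**5. Large true improvement.** Later scores were lowered by one latent SD:

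| r | 10% zeros | 30% zeros | 50% zeros |
|---|---|---|---|
| 0 | 40.6% | 66.1% | 82.0% |
| 0.3 | 47.0% | 66.0% | 78.7% |
| 0.5 | 52.1% | 67.7% | 78.1% |
| 0.7 | 57.9% | 71.1% | 79.4% |
| Percent change of group means | 55.4% | 67.3% | 75.7% |

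For r of 0.3 or more the largest gap is 55.4 − 47.0 = 8.4 points. At r = 0 it is 55.4 − 40.6 = 14.8 points. The sign is right in every cell.

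**The case against.** The strongest reply is that little depends on this statistic. The endpoints are score changes, not percentages. The SAP makes the MMRM of change primary and attaches no hypothesis or p-value to % improvement. The median percentage, observed values and absolute changes stand in the same summaries. That stands: primary inference is not touched, and calling these percentages headline results is an inference that the documents do not support. Two qualifications apply. The MMRM paragraph in SAP 4.5.1.2 names domain and total scores only, although Protocol 8.3.2 also covers single items. And the QoL outputs concerned are topline.

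A second reply is that a no-change scenario is not this trial, since the protocol expects colds to resolve. This also stands in part. Step 5 shows a modest gap and a correct sign when improvement is large. A reader might infer that the trial's percentages will have the wrong sign; the calculations show that only as possible where little changes, such as an early day or a mild item.

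Third, the documents do not show that many subjects have a zero baseline, nor that the values of the remaining subjects are false. Both might be inferred. The share is unknown, and the distortion is in the group mean, not in each subject's own percentage.

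Fourth, worst-case limits alone do not separate the items from the scores where subject-level percentages would be kept. The total score can reach 100 × (8 − 133)/8 = −1,562% and the symptom domain 100 × (8 − 70)/8 = −775%. This is correct, and is why the median should lead for those two.

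Finally, a formula, a zero-baseline rule and the number evaluable would be a lighter repair. They would cure the undefined values and disclose the denominator, but not the distorted mean.

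**Conclusion.** The point holds as a defect in a descriptive summary. As written, the measure cannot be computed for every subject on 18 of 19 items and the QoL domain. Leaving out zero baselines gives a mean that can be biased either way: under no change, about −33% to +26% at correlation 0, −26% to +16% at 0.3, −20% to +9% at 0.5 and −13% to +4% at 0.7. At intermediate shares of zeros the two biases partly cancel.

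These sizes rest on assumptions that the documents can neither confirm nor refute: 10% to 50% zero baselines, non-zero scores uniform on 1-7, a latent normal correlation, and omission of zero baselines. The absence of a guaranteed non-zero baseline rests on the documents alone.

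The direction is not fixed. A reader might infer that the plan flatters the product, but with few zeros the bias runs against it. Cough always has a non-zero baseline of at least 5 in eligible subjects, and the total and symptom domain scores one of at least 8.

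**What to change.** Amend SAP 4.5.1.1 and 4.5.1.2 as follows.

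- Define % improvement as 100 × (baseline − Day t)/baseline.
- Keep subject-level values only for the total score, the symptom domain score and the cough item, with the median as the main summary for the first two.
- For the QoL domain and the other 18 items, report 100 × (mean baseline − mean Day t)/mean baseline, over mITT subjects with both values, with a bootstrap 95% confidence interval.
- Show the number of subjects with baseline 0 for each of these scores.

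The cost is SAP wording and minor programming, with no new data. Some percentages will look less favourable than under the present plan and some more.
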